Verification of eligibility will be performed and appropriate documentation of informed consent will be documented for all subjects enrolled into the study. The timeliness of Adverse Event and Serious Adverse Event reporting will be monitored to ensure regulatory compliance. All case report forms (CRF) for the first subject enrolled into the study will be monitored for completeness and quality by comparing data in the case report forms to data in the source documents. Thereafter, a minimum of 10% of enrolled subjects' CRFs will be monitored for completeness and quality by comparing data in the case report forms to data in the source documents.

Data Safety Monitoring Plan

A qualified physician not associated with this particular protocol will be chosen as medical monitor for this study. The medical monitor will meet with the PI or designee and review study data/progress a minimum of every 6 months; more often at the discretion of the PI and/or medical monitor.

The medical monitor is required to review all unanticipated problems involving risk to subjects or others, unanticipated serious adverse events and all subject deaths associated with the protocol and provide an unbiased written report of the review.

At a minimum, the medical monitor should comment on the outcomes of the event or problem, and in the case of unexpected serious adverse event or death, comment on the relationship to participation in the study. Based on the review of these events, the monitor should make a recommendation regarding study continuation. All decisions regarding study continuation, modification, or termination will be reported immediately or

annually, as appropriate, to the IRB, FDA, and other appropriate agencies. Reports for events determined by either the investigator or medical monitor to be possible or definitely related to study participation and reports of events resulting in death should be forwarded in compliance with current IRB policy and applicable federal regulations.

Adverse Event Reporting

Safety and tolerability for the study drug will be assessed according to the Common Terminology Criteria for Adverse Events v4.0 (CTCAE published October 6, 2009). The principal investigator or designee will review adverse events closely and assess the event's relationship to study procedures to determine whether the event is unrelated or, unlikely, possibly, probably or definitely related to the study procedures, especially in relation to the underlying disease and baseline lab values for the patient. All adverse events (except as specified below) will be recorded on case report forms and reported in compliance with CCHMC IRB and federal guidelines. All expected and unexpected Grade 3 and higher adverse events occurring during this study up through 30 days following the last dose of maraviroc will be recorded on the case report forms, unless directly attributable to the underlying disease. The principal investigator will review each event and assess its relationship to study events to determine whether the event is unrelated or, unlikely, possibly, probably or definitely related to the study therapy.

Additionally for this study, events as previously identified as resulting from administration of a stem cell transplant will be considered as expected. The transplant regimen is well known to commonly affect systems such as the hematologic, immunologic and gastrointestinal systems. The following are known complications of transplant- disseminated intravascular coagulation, febrile neutropenia, hemolysis, thrombotic thrombocytopenic purpura, adrenal insufficiency, colitis, constipation, diarrhea, enterocolitis, gastrointestinal pain, malabsorption, mucositis, nausea, pancreatitis, vomiting, dyspepsia, fever, pain, cholecystitis, allergic reaction, serum sickness, upper respiratory infection, urinary tract infection, weight gain/loss, acidosis, alkalosis, anorexia, dehydration, glucose intolerance, iron overload, generalized muscle weakness, reversible posterior leukoencephalopathy syndrome, bladder spasms, cystitis, hematuria, urinary frequency, urinary urgency, irregular menstruation, pruritis, hypertension, purpura, and petechiae. For the purposes of the study, the listed events that are < grade 3 will not be considered adverse events.

Hematologic toxicities which are attributable to the underlying hematological disease will not be considered adverse events; however, grade ≥ 3 neutropenia will be documented and assessed for attribution.

In the event that any of these known complications of transplant or hematologic toxicities are thought to be at least possibly attributable to the study drug, the event will be recorded and subsequently reported to the FDA and IRB according to current reporting requirements.

Adverse reactions must be reported to the principal investigator who is responsible for the reporting to the Cincinnati Children's Hospital Medical Center IRB according to current guidelines. All Adverse Event reporting is to comply with the current CCHMC IRB policy and applicable federal regulations. If any serious adverse events occur, current guidelines will be followed for expedited reporting to the IRB and FDA.

All serious and medically significant adverse events considered related to maraviroc by the investigator will be followed until resolved or considered stable.

Expected events are those that have been previously identified as resulting from administration of the protocol therapy, those that can be contributed to the underlying condition, and/or those associated with transplant. An adverse event is considered unexpected, for reporting purposes only, when either the type of event or the severity of the event is not listed in the drug package insert, consent and/or protocol.

Medical conditions/diseases present before starting study drug are only considered adverse events if they worsen after starting study drug. Abnormal laboratory values or test results constitute adverse events only if they induce clinical signs or symptoms, are considered clinically significant, or require therapy as determined by the PI.

Other research studies

Patients enrolled in this study may be enrolled of any one of the several approved therapeutic and non-therapeutic BMT research studies. There is no foreseen increase in the cumulative risk to the patient enrolled in this study as well as in a therapeutic or non-therapeutic BMT research study.

Risk assessment recommendation

This study will be of more than minimal risk but with potential for direct benefit to participants

Potential Benefits

The direct potential benefit to patients will be reduction in the incidence of acute visceral graft versus host disease.

Potential Risks, Discomforts, Inconveniences and Precautions

There are risks to the patients which include allergic reaction to the drug, hepatotoxicity, gastrointestinal discomfort, need for placement of a nasogastric tube for reliable administration of the drug and possible infectious complications. Safety data for long term use of Maraviroc are not available.

Confidentiality

Any copies of research records will be kept in locked files and any information stored on computer will be password protected. The information from the study may be published; however, subjects will not be identified in such publications. The publication will not contain information about the subjects that would enable someone to determine their identity as a participant without the subject's authorization.

The Institutional Review Board may have access to these records.

The use of clinical information for research purposes and the protection of privacy will be done in compliance with Cincinnati Children's Hospital Medical Center HIPAA requirements.

Period of Time Estimated to Complete Project as Described

Approximately 65 patients will be enrolled on study, which will occur over a time frame of approximately 5 years.

Funding

There is no outside funding for this study. Patients will not be charged for the drug, pharmacokinetic or pharmacodynamic assays.

Payment for Studies

There will be no compensation to patients.

Methods to be used in procuring consent of subjects

[name] or one of the other Bone Marrow Transplant Physicians who are co-investigators will consult with the patient and/or the parent/legal guardian to explain the procedures, risks and benefits of the study at the patient/parent's level of understanding. Opportunity will be given to consider the study and have questions answered. Information will be given in a written format in the form of a description of the study, which will include a signature space for consent to be given (see attached patient/parent document).

Prior to the initiation of the study, acknowledgement of the receipt of this information and the subject's freely tendered offer to participate will be obtained in writing from each subject in the study. Participation is voluntary, and all subjects/parents/guardians will give informed consent to participate. Assent will be obtained from patients 11-17 years of age. Information will also be given verbally, and all patients and/or parents will have an opportunity to ask questions.

While we do not plan on targeting non-English speaking patients for enrollment on this study, we do periodically have patients who speak Spanish or Arabic. We will not exclude these patients from this study. We will use a short form or fully translated consent (as applicable) according to the process outlined in the Clinical Management and Resource Support Core Standard Operating Procedures (SOP).

Adverse effects of maraviroc reported in HIV populations-

Likely (>10% of patients):

- Central nervous system: Fever (12%)
- Respiratory: Upper respiratory tract infection (20%), cough (13%)

Less Likely (2-10% of patients):

- Cardiovascular: Vascular hypertensive disorder (3%).
- Central nervous system: Dizziness (8%), insomnia (7%), consciousness disturbances (4%), depression (4%), pain (4%).
- Dermatologic: Rash (10%), pruritus (4%), folliculitis (3%), skin neoplasms (benign; 3%), dermatitis (3%).
- Endocrine & metabolic: Lipodystrophy (3%).
- Gastrointestinal: Abdominal pain (8%), appetite disorders (7%), constipation (5%), dyspepsia (3%), stomatitis (3%).
- Genitourinary: Urinary tract/bladder symptoms (3% to 5%), genital warts (2%).
- Hematologic: Neutropenia (grades 3/4: 4%).
- Hepatic: Transaminases increased (grades 3/4: 2% to 5%), bilirubin increased (grades 3/4: 6%).
- Neuromuscular & skeletal: Parasthesia (5%), sensory abnormality (4%), muscle pain (3%), peripheral neuropathy (3%).
- Respiratory: Bronchitis (6%), sinusitis (6%), breathing abnormality (3%), bronchospasm (2%), respiratory tract/sinus disorder (2%).
- Miscellaneous: Herpes infection (7%), sweat gland disturbances (5%), influenza (2%).

Rare but Serious (<2% of patients):

Abdominal neoplasm, acute cardiac failure, anal cancer, angina, basal cell carcinoma, Bowen's disease, C. difficile colitis, cerebrovascular accident, cholangiocarcinoma, cholestatic jaundice, coronary artery disease, coronary artery occlusion, creatine kinase increased, esophageal candidiasis, esophageal carcinoma, hepatic cirrhosis, hepatic failure, hepatotoxicity, liver metastases, lymphoma, MI, myocardial ischemia, myositis, osteonecrosis, pneumonia, rhabdomyolysis, rhinitis, septic shock, squamous cell carcinoma, syncope, tongue neoplasm, viral meningitis

CCHMC IRB# 2014-1221

Version: 03.23.2018

References cited-

1. Weisdorf D. GVHD the nuts and bolts. Hematology / the Education Program of the American Society of Hematology American Society of Hematology Education Program 2007:62-67.

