3. Abnormal ALT (≥ 5 X ULN) on day -3. (This criterion is to be assessed at study enrollment, but it will be confirmed again prior to the first dose of maraviroc)
4. Individuals who are HIV positive will not be enrolled in the study.

Treatment Plan

Dose and schedule of Maraviroc administration-

Maraviroc administration will start on day -3 and will end on day +30 after stem cell transplant, making the total number of days of drug administration 34 days. Our goal is to have steady state Maraviroc concentrations before stem cell infusion (on day 0) and continuing during the period of engraftment. The day of planned stem cell infusion will be recorded as day zero. If the stem cell infusion is given over 2 days, the first of those 2 days will be considered as day zero. Maraviroc will be administered twice daily orally or via enteral tube. Maraviroc absorption is somewhat reduced with ingestion of a high-fat meal; however, it can be given with or without food.

Dosing of Maraviroc will be based on body surface area, which will be assessed prior to starting maraviroc. This is based on the current congenital HIV trial using Maraviroc. We hypothesize that the optimal dose and exposure (as measured by the area under the concentration-time curve; AUC) for GVHD prophylaxis will likely conform to the optimal dose for the congenital HIV population (Table1). However, we recognize that stem cell transplant patients are more highly catabolic and have significantly more

concomitant medications than HIV patients, so are aware that we may find important PK differences.

BSA (m ²)	Dose of Maraviroc to be administered orally
<0.22	40 mg bid
0.2-0.43	100 mg bid
0.44-0.72	200 mg bid
0.73-1.19	300 mg bid
1.20-1.30	300 mg bid
1.31-1.73	300 mg bid
>1.73	300 mg bid

Table 1. Dosing of Maraviroc based on BSA [32].

Drug interactions with maraviroc occur with strong CYP3A4 inducers and inhibitors so these may not be used during the period of administration of maraviroc.

Enzyme Inducers	Enzyme Inhibitors
Carbamazepine	Amiodarone
Phenobarbital	Clarithromycin/Erythromycin
Phenytoin	Azoles (Keto/ Itra/ Vori/Posaconazole)
Rifampin	Verapamil
Rifabutin	Diltiazem
St. John's Wart	Grapefruit Juice
	Antiretroviral medications

Table 2. List of concomitant medications (CYP3A4 inducers and inhibitors) not allowed at enrollment or during study treatment

Adverse effects of Maraviroc

For a complete list of adverse effects, please see page 18 of protocol [23].

Study design-

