For the first part of the study, where full AUC analysis will be performed to verify the dose, we anticipate initially enrolling 12 patients to achieve 12 dose verifications. Any patients who do not achieve a complete PK data profile (i.e. due to suboptimal dose or incomplete course of study drug) will be replaced to achieve 12 dose verifications. The total number of patients will still remain 65 (Phase I and Phase II). The age of enrollment for these patients will be limited to 2-12 years old. This age restriction has been imposed because adult dosing for maraviroc in the stem cell transplant setting has already been established and it is likely that teenagers metabolize the drug similar to adults. The second part of the study, where full AUC analysis will not be conducted, will enroll the remaining patients between the ages 2-40 years.

We will enroll eligible patients and maraviroc will be administered as per study rules. Area under the concentration-time curve (AUC) determination will be performed on days 0 +/- 3 days and 10 +/- 3 days to account for weekends, national holidays or clinical deterioration not allowing for scheduled blood draws on the specified days. PK analysis will be performed after the first 3 patients. As per our study design graph, this is not an "interim" analysis, but an analysis to verify PK target attainment which then will drive either further observation or dose escalation. See Figure 1.

[figure not shown]

Figure 1. Study design

Pharmacokinetic measurement and analysis-

Blood for PK will be collected on day 0 +/- 3 days and Day 10 +/- 3 days. Complete PK profile (full AUC) will be performed on these days (see time points below). Evaluation of maraviroc trough levels will also be done routinely on all patients on study on days 0,7,14 and 21 in order to collect additional PK data, verify compliance and allow for additional dose corrections if necessary.

Target AUC/12 hours= $\geq 100\text{ng/mL}$ (based on HIV data)

PK processing will be performed at University of North Carolina's Clinical Pharmacology and Analytical Chemistry Laboratory using mass spectrometer with HPLC separation.

Plasma Maraviroc concentration data will be analyzed by compartmental and non-compartmental analysis with the help of [name], Director of Pediatric Pharmacology Research Unit (PPRU) at CCHMC, and parameter estimates generated will include clearance, half-lives, and volume of distribution along with area under the curve (AUC).

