 - c. Other grade 4-5 toxicity , unless clearly related to stem cell transplant and not to study drug, including but not limited to veno-occlusive disease of the liver, acute graft versus host disease, autoimmune cytopenias, infectious complications due to stem cell transplant, or organ toxicities due to conditioning regimens.

BSA	Original Dose	Dose escalation	Value increment/dose
<0.22	40 mg bid	50 mg bid	+ 10 mg
0.2-0.43	100 mg bid	120mg bid	+ 20 mg
0.44-0.72	200 mg bid	250 mg bid	+ 50 mg
0.73-1.19	300 mg bid	350 mg bid	+ 50 mg
1.20-1.30	300 mg bid	350 mg bid	+ 50 mg
1.31-1.73	300mg bid	350 mg bid	+ 50 mg
>1.73	300 mg bid	350 mg bid	+ 50 mg

Table 4. Table showing doses and increments for dose escalation of Maraviroc.

Stopping Rules

1. If the incidence of Grade 2-4 acute GI or Liver (visceral) graft versus host disease is greater than 50% in the first 20 subjects by day +100, the study will be stopped. Enrollment will not stop while the analysis is being conducted.

2. If 3 out of 6 subjects experience DLT by day +30 as defined above at the initial dose in the first phase (AUC analysis) of the study, the study will be stopped. Enrollment will not be suspended while the analysis is being conducted.
3. The study will be halted for any grade 4 liver toxicity occurring within 30 days of study drug administration and without clear attributable alternative cause. Enrollment will be suspended while an analysis of the toxicity is being conducted. Enrollment will only restart with approval of the Medical Monitor, IRB and FDA. (Of note: any grade 3 liver toxicity (ALT > 5xULN or Total Bilirubin > 3xULN), regardless of cause, will lead to permanent discontinuation of Maraviroc for that specific patient, but enrollment will continue.)

Primary study end points

1. Feasibility
2. GVHD incidence by day +100 (all grades)
3. pK target >100ng/ml

Secondary Study end points

1. Overall survival by day +100
2. Graft failure by day + 100
3. Primary disease relapse by day +100
4. Incidence of toxicities either due to drug or transplant
5. Infectious complications which include asymptomatic viremias for EBV, Adenovirus, CMV, and/or viral disease, bacterial and fungal infections as documented by blood cultures.
6. Time to neutrophil and platelet engraftment

GVHD will be graded according to IBMTR criteria as shown in table 5 [33]-

	Stage 0	Stage 1	Stage 2	Stage 3	Stage 4

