Skin	No rash	Rash < 25% BSA	Rash 25-50% BSA	> 50% BSA or generalized erythroderma	Bullae or desquamation
GI	< 500 ml diarrhea	501-1000 ml diarrhea/day	1001-1500 ml diarrhea/day	> 1500 ml diarrhea/day	Abdominal pain and ileus
Liver	Bilirubin < 2 mg/dL	2.1-3 mg/dL	3.1-6 mg/dL	6-15 mg/dL	> 15 mg/dL

Grading		Grade 1	Grade 2	Grade 3	Grade 4
Skin		1	2	3	4
GI		0	1-2	3	4
Liver		0	1-2	3	4

Table 5. Grading and staging of GVHD.

Diagnosis of GVHD is mostly clinical and as such will be on the discretion of the treating physician. Biopsies may aid the diagnosis whenever clinically indicated but are not required in the study.

Clinical Data to be Collected and Reported:

Patients' medical information will be systematically and prospectively collected as is usual for all SCT patients. The data collected will include, but not be limited to-

1. Demographics including age, gender, weight, and height.
2. Underlying diagnosis
3. Specifics of HCT (preparative regimen, type of graft, cell dose, GVH prophylaxis, HLA type and donor relation etc.).
4. Details of engraftment (timing, failure to engraft, loss of graft)
5. Adverse effects directly related to maraviroc and transplant course
6. Onset of GVHD, grade, organ involved and treatments used by day +100
7. Whole blood donor chimerism
8. Infectious complications which include asymptomatic viremias for EBV, Adenovirus, CMV, and viral disease, bacterial and fungal infections as documented by blood cultures or bronchoalveolar lavage cultures/PCRs.
9. Overall survival at day +100
10. Incidence of relapse of primary disease by day +100

Study calendar

All testing below is part of standard evaluation for all patients undergoing allogeneic stem cell transplant and is not dependent on study enrollment, unless marked by “*”

	Enrollment	D-3	D 0 (± 3 days)	D +7 (± 2 days)	D+10 (± 3 days)	D+14 (± 3 days)	D+21 (+ 3 days)	D+30 (+ 7 days)	Monthly after day +30 until day+ 100 (± 7 days)
Informed Consent*	x								
History and physical examination	x	x	x	x	x	x	x	x	x
GVHD prophylaxis	x	x	x	x	x	x	x	x	x
CYP3A4 enzyme inducers or inhibitors *	x	x	x	x	x	x	x	x	
Acute GVHD evaluation and treatment								x	x
Full AUC analysis (dose verification part)*			X		X				
pK trough*			X	x		x	x		
pD*	X		X			X			
LFTs/CBCD/ Renal profile	x	x	x	x	x	x	x	x	x
Adverse event evaluation*		Continuous							
Compliance*		x	x	x	x	x	x	x	
Chimerism(whole blood)								x	Day + 100
Survival									Day + 100

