Study calendar for blood draws for patients undergoing formal AUC analysis-

Days	AUC	Trough drug level	Pharmacodynamic assessment
Pretransplant			x
Day 0	X (± 3 days)		X (± 3 days)
Day 7		x (± 2 days)	
Day 10	X (± 3 days)		
Day 14		x (± 3 days)	X (± 3 days)
Day 21		x (± 3 days)	

Table 6. Study calendar for blood draws for patients undergoing formal AUC analysis

For patients enrolled after maraviroc dose has been verified, the schedule for lab draws is shown on Table 7.

Days	Trough drug level	Pharmacodynamic assessment
Pretransplant		x
Day 0	x (± 3 days)	X (± 3 days)
Day 7	x (± 2 days)	
Day 14	x (± 3 days)	X (± 3 days)
Day 21	x (± 3 days)	

Table 7- Study calendar for blood draws for patients on second phase of study (after PK study complete and dose verified)

Volume of Blood Draws-

For pharmacokinetic analysis, we will need approximately 3 ml of blood, to be collected in an EDTA tube. Real time data results will be available to allow for dosing changes to

be made after the first 3 patients. For pharmacodynamics analysis, we will need 2 ml blood in a sodium heparin tube.

Discontinuation of therapy-

Since most patients experience severe toxicities while undergoing an allogeneic SCT, it will be the investigator's responsibility to determine whether certain adverse events are related to the study drug or not based on previous studies using the agent and the current labeling. Common Terminology Criteria for Adverse Events (CTCAE) version 4.0 will be used to report toxicities.

The following events will mandate stopping Maraviroc for a specific patient;

- Grade 3 liver toxicity (ALT > 5xULN or Total Bilirubin > 3xULN) regardless of cause

Maraviroc will not be restarted in these cases.

The following events will mandate holding Maraviroc therapy on a specific patient:

1. Grade 3 or higher toxicity (exclusive of liver toxicity, see section above), not attributable to underlying disease.
2. Infection, which requires treatment with a strong CYP450 inducer or inhibitor (predicted to adversely interact with Maraviroc) such as rifampin.
3. Drop in renal function to creatinine clearance <40 ml/min as measured by GFR or cystatin C.

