The drug can be restarted at the same dose after full recovery from the AEs. Maraviroc will be discontinued if the AE recurs after re-challenge. Any grade 3 liver toxicity (ALT > 5xULN or Total Bilirubin > 3xULN) regardless of cause will lead to permanent discontinuation of Maraviroc for that patient. The study will be halted for any grade 4 liver toxicity occurring within 30 days of study drug administration without clear attributable alternative cause (see stopping rules for details). Re-challenge is not permissible in the event of Grade 3 or higher liver toxicity (ALT > 5xULN or Total Bilirubin > 3xULN) regardless of cause. Any grade 1 or 2 toxicities related to study drug will not require study drug to be held.

Early termination of study drug-

Treatment will continue unless one of the following criteria applies:

1. A dose limiting toxicity (DLT) occurs. A DLT is defined as either-
 - a.) Non-engraftment by day 30, if assessed by the investigator to be related to the study drug. Engraftment is defined as the first of three consecutive measurements of ANC>500/mcL over 3 or more days.
 - b.) Grade 4 liver abnormalities, once other causes for liver toxicity have been ruled out.
 - c.) Other grade 4-5 toxicity determined by the investigator to be related with high probability to the study drug.
2. Any grade 3 or higher liver toxicity (ALT> 5xULN or Total Bilirubin > 3xULN) regardless of cause:
 - a. Any grade 3 liver toxicity (as defined above) will lead to permanent discontinuation of Maraviroc for that patient.
 - b. The study will be halted for any grade 4 liver toxicity occurring within 30 days of study drug administration without clear attributable alternative cause. (See stopping rules for specific details.)
3. Patient decides to withdraw from the study due to inability to take the drug.
4. Poor compliance to drug (missing either 6 consecutive doses (3 days) or 12 intermittent doses in the entire administration period (< 80% compliance)).

Patients removed from study for unacceptable adverse events will be followed until the adverse event resolves or stabilizes.

Toxicity Monitoring-

Maraviroc is generally well tolerated in children as noted in the phase 1 congenital HIV trial. However, a black box warning for hepatotoxicity exists. Therefore, liver function tests will be monitored on patients while on maraviroc every 48 hours until day+30 (+ 7 days).

General concomitant medication and supportive care guidelines

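### Entry screens the liver on ALT alone, yet total bilirubin above 3×ULN permanently stops the drug, so a patient can be eligible and dosed while already over the stop limit

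*Combined protocol and SAP*

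**What the plan says.** **Entry.** Exclusion Criteria item 3 is the only liver criterion: "Abnormal ALT (≥ 5 X ULN) on day -3". It is assessed at enrollment and confirmed before the first dose. None of the six inclusion or four exclusion criteria mentions bilirubin, and the inclusion criteria admit every diagnosis and every conditioning regimen.

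**Stop.** The section on discontinuation of therapy requires the drug to be stopped for "Grade 3 liver toxicity (ALT > 5xULN or Total Bilirubin > 3xULN) regardless of cause". Stopping Rules item 3 says that such an event "will lead to permanent discontinuation of Maraviroc for that specific patient", and the section on early termination of study drug repeats the rule. The text after the list of holding events adds: "Re-challenge is not permissible in the event of Grade 3 or higher liver toxicity".

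**Testing.** The study calendar has a row "LFTs/CBCD/ Renal profile" marked at enrollment and at D-3. Toxicity Monitoring states that "liver function tests will be monitored on patients while on maraviroc every 48 hours until day+30 (+ 7 days").

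**Purpose of the schedule.** Dosing starts on day -3, twice daily, and ends on day +30. The dosing section gives the reason: "Our goal is to have steady state Maraviroc concentrations before stem cell infusion (on day 0) and continuing during the period of engraftment".

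**PK part.** The study design section says: "Any patients who do not achieve a complete PK data profile (i.e. due to suboptimal dose or incomplete course of study drug) will be replaced". The overall total stays at 65.

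**The concern.** An entry rule should not admit a patient whom the protocol's own safety rule bars from the drug. On ALT it does not. On bilirubin it can, because only one limb of a two-limb stop rule was carried back to eligibility.

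Two things are at stake. The first is the patient, who would start a drug with a boxed hepatotoxicity warning while above the protocol's liver limit. If the stop then comes before infusion, none of the intended peri-engraftment exposure is delivered, so the patient carries the risk with little prospect of benefit. The second is a place in the PK part: a patient stopped before day 0 cannot supply the second AUC profile and must be replaced from within the fixed 65.

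The protocol gives no reason to treat bilirubin as the minor limb. Its list of effects in HIV patients on maraviroc puts grade 3/4 bilirubin increases at 6% and grade 3/4 transaminase increases at 2% to 5%. Those are on-drug rates and say nothing about how often bilirubin is raised at baseline in transplant patients.

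**Working it through.** The plan states no figure to reproduce. The check is a comparison of rules, followed by a dose count.

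**1. Entry and stop limits side by side**

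| Marker | Excluded at entry | Permanent stop on treatment | Can a patient start above the stop limit? |
|---|---|---|---|
| ALT | ≥ 5×ULN | > 5×ULN | No; every value that triggers the stop is excluded |
| Total bilirubin | no limit | > 3×ULN | Yes |

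Take ALT 1×ULN and total bilirubin 4×ULN on day -3. Exclusion 3 is not met, because 1 < 5. No other criterion applies. The stop limit is exceeded, because 4 > 3. The patient is eligible and already over the limit.

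**2. Is the gap closed elsewhere?** Liver tests are scheduled at D-3, so a bilirubin value should exist. No rule makes starting the drug depend on it; the pre-dose confirmation concerns the ALT criterion only.

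**3. Exposure of such a patient**

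Inputs: 34 days of administration and twice-daily dosing (dosing section); liver tests every 48 hours on drug (Toxicity Monitoring). Assumptions: doses 12 hours apart, and the 48-hour interval counted from the first dose.

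- Planned doses: 34 × 2 = 68.
- Day -3 bilirubin acted on at once: 0 or 1 dose, at most 1/68 = 1.5%.
- Stop at the first 48-hour test: 48/12 = 4 doses (hours 0, 12, 24, 36), 4/68 = 5.9%.
- As above, with the hour-48 dose given before the result is back: 5/68 = 7.4%.
- Day of that stop: day -3 plus 48 hours = day -1, before infusion on day 0.

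**4. Consequence in the PK part.** The second full AUC is due on day 10 ± 3 days, so the earliest date is 10 − 3 = day 7. A patient stopped on day -1 cannot provide it and has to be replaced.

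**5. Number affected.** The documents do not say how often bilirubin exceeds 3×ULN with ALT below 5×ULN on day -3. The count cannot be computed, and it could be zero.

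**The case against.** The other side accepts the comparison of the rules and disputes how much it matters.

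- **The day -3 panel already contains the problem.** If the stop rule applies whatever the cause, a high day -3 bilirubin bars the drug at once and exposure is 0 or 1 dose. The 4- or 5-dose case needs that result to be missing or not acted on, and it also needs the 48-hour clock to start at the first dose, which the protocol does not say. This stands as a limit on size. It does not close the gap: no rule ties the bilirubin result to starting, and a patient stopped at once has still been enrolled for a drug the protocol will not let them take.
- **A raised baseline value may not be a toxicity.** The section on adverse event reporting counts pre-existing conditions as adverse events only if they worsen, and attribution takes baseline laboratory values into account. But that section governs reporting. The stop rule is a laboratory threshold applied irrespective of cause, with no written exception for baseline. If the lenient reading were adopted, such a patient could stay on the drug for up to 34 days while above 3×ULN, which is worse. An entry limit removes the ambiguity.
- **Frequency and harm are not shown.** Correct. The only rates available are on-drug rates in HIV patients. The protocol also reports that, in the earlier transplant study, liver abnormalities did not return when the drug was resumed, and that post-marketing surveillance had registered no significant events. A lost PK profile is already covered by the replacement rule.
- **The fix has a price.** Applied at enrollment, a bilirubin limit could turn away patients whose value would settle before dosing. This stands, and the fix takes it into account.

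**Conclusion.** The concern holds. One of the two limbs of the permanent liver stop has no counterpart at entry, so an eligible patient can receive the first dose while already over the limit.

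Per affected patient, exposure is 0 to 1 dose if the day -3 result is used, and 4 to 5 of 68 doses (5.9% to 7.4%) if the stop waits for the first 48-hour test. The upper figures rest on 12-hourly dosing and on counting the interval from the first dose. All of them take the stop rule to apply to a value already raised at baseline, as its wording implies, and the later-stop figures also assume that bilirubin is still above 3×ULN at the 48-hour test.

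The number of patients affected is unknown and may be small. No effect on the GVHD estimate is claimed. It should be fixed because it is an inconsistency in a safety rule that can be removed without adding a test, not because a large effect has been shown.

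**What to change.** Reword exclusion 3 to exclude patients with ALT ≥ 5×ULN or total bilirubin > 3×ULN, assessed at enrollment and confirmed before the first dose. The bilirubin limit is the protocol's existing stop threshold, and the timing is that already used for ALT.

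The cost is a one-line amendment. No test is added, because liver tests are already on the calendar at enrollment and D-3. A few patients, a number the documents do not allow one to compute, become ineligible. Under the reading in which a baseline value does not itself trigger the stop, some of them might have fallen below 3×ULN by day -1 and continued.

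If losing patients with a transient elevation at enrollment is a worry, the bilirubin limit can be applied at the pre-dose check alone; that still prevents dosing above the stop limit. A stop rule adjusted for baseline would also remove the contradiction, but it would permit dosing above 3×ULN and would need a new threshold to be justified, so the entry limit is the simpler choice.
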